4. PARTICIPANT ENTRY

4.1 RECRUITMENT

The reviewing physician will approach potentially eligible patients for the study during a clinic they are routinely attending after determining whether they meet the inclusion /exclusion criteria. All patients will be spoken to in person during their clinic appointment. Potential participants will have the duration of the morning clinic to decide whether or not to participate in the study. It is standard practice to offer and deliver a corticosteroid injection within a 20 minutes clinic appointment, without pre-warning that this may be appropriate or available within clinic. Patients rarely need additional time to decide if they would like this on the day treatment.

A verbal explanation of the trial and why the patient has been invited to participate will be given, together with a Participant Information Sheet (Appendix 2) and a copy of the Patient Consent Form (Appendix 3). The patient will also be given the contact details of the Hand and Wrist Registrar/ [name] should they wish to seek further information about the study.

Recruitment will continue until 100 patients have been randomised and received the study intervention.

4.2 PRE-REGISTRATION EVALUATIONS

The patient participation record (Appendix 4) must be completed prior to inclusion; however there are no further pre-registration tests required for the patient to be included.

4.3 INCLUSION CRITERIA

- Male or female ages $>/= 18$ years
- A clinical diagnosis of trigger finger, de Quervains tenosynovitis or carpal tunnel syndrome made by a consultant physician.
 - Trigger finger: A diagnosis made on a history of triggering together with clinical findings of pain localised to the first annular pulley along with triggering of the affected digit
 - De Quervains tenosynovitis: A diagnosis made on clinical examination findings of pain over the first dorsal compartment, swelling localised to the first dorsal compartment and a positive Finklestein test.
 - Carpal tunnel syndrome: A diagnosis made on a history of intermittent paraesthesia in the radial 3.5 digits, with nocturnal symptoms and subjective sensory impairment and thumb weakness.
- Treatment with corticosteroid injection is recommended by the doctor and agreed by the patient
- Patient is willing and able to give informed consent for participation in the study

4.4 EXCLUSION CRITERIA

- Previous surgery for the condition being treated at the desired location of injection*
- Previous steroid injection for the condition being treated at the desired location of injection*
- Clinical suspicion of local or systematic sepsis or infection
- History of hypersensitivity to the corticosteroid or local anaesthetic
- Pregnant or breast-feeding females
- Unable to understand and complete self-report questionnaires written in English

*Previous surgery or a corticosteroid injection elsewhere in the hand or wrist does not exclude the patient from the trial

4.5 WITHDRAWAL CRITERIA

Patients are able to withdraw from the study at any stage without prejudice.

5. ADVERSE EVENTS

5.1 DEFINITIONS

Term	Definition
Adverse Event (AE)	Any untoward medical occurrence in a participant to whom a medicinal product has been administered, including occurrences which are not necessarily caused by or related to that product.
Adverse Reaction (AR)	An untoward and unintended response in a participant to an investigational medicinal product which is related to any dose administered to that participant. The phrase "response to an investigational medicinal product" means that a causal relationship between a trial medication and an AE is at least a reasonable possibility, i.e. the relationship cannot be ruled out.

	All cases judged by either the reporting medically qualified professional or the Sponsor as having a reasonable suspected causal relationship to the trial medication qualify as adverse reactions.
Serious Adverse Event (SAE)	
A serious adverse event is any untoward medical occurrence that:
 
 • results in death • is life-threatening • requires inpatient hospitalisation or prolongation of existing hospitalisation • results in persistent or significant disability/incapacity • consists of a congenital anomaly or birth defect 
Other 'important medical events' may also be considered serious if they jeopardise the participant or require an intervention to prevent one of the above consequences.
 
NOTE: The term "life-threatening" in the definition of "serious" refers to an event in which the participant was at risk of death at the time of the event; it does not refer to an event which hypothetically might have caused death if it were more severe.

Serious Adverse Reaction (SAR)	An adverse event that is both serious and, in the opinion of the reporting Investigator, believed with reasonable probability to be due to one of the trial treatments, based on the information provided.
Suspected Unexpected Serious Adverse Reaction (SUSAR)	
A serious adverse reaction, the nature and severity of which is not consistent with the information about the medicinal product in question set out:
 
 • in the case of a product with a marketing authorisation, in the summary of product characteristics (SmPC) for that product • in the case of any other investigational medicinal product, in the investigator's brochure (IB) relating to the trial in question

Medical judgement should be exercised in deciding whether an AE is serious in other situations. Important AEs that are not immediately life-threatening or do not result in death or hospitalisation but may jeopardise the subject or may require intervention to prevent one of the other outcomes listed in the definition above, should also be considered serious.

5.2 REPORTING PROCEDURES

All adverse events should be reported. Depending on the nature of the event the reporting procedures below should be followed. Any questions concerning adverse event reporting should be directed to the Chief Investigator in the first instance.

5.2.1 Non serious AEs

All such events, whether expected or not, should be recorded.

5.2.2 Serious AEs

"All SAEs / SUSARs occurring from the time of written informed consent until 24 hours post cessation of trial treatment must be recorded on the SAE Form and e-mailed to the Sponsor within 24 hours of the research staff becoming aware of the event. Once all resulting queries have been resolved, the Sponsor will request the original form should also be posted to the Sponsor and a copy to be retained on site.

For each SAEs / SUSARs the following information will be collected:

- full details in medical terms and case description
- event duration (start and end dates, if applicable)
- action taken
- outcome
- seriousness criteria
- causality (i.e. relatedness to trial drug / investigation), in the opinion of the investigator
- whether the event would be considered expected or unexpected.

Any change of condition or other follow-up information should be faxed to the Sponsor as soon as it is available or at least within 24 hours of the information becoming available. Events will be followed up until the event has resolved or a final outcome has been reached.”

5.2.3 Suspected Unexpected Serious Adverse Reaction (SUSAR)

“All SAEs assigned by the PI or delegate (or following central review by the CI and sponsor) as both suspected to be related to IMP-treatment and unexpected will be classified as SUSARs and will be subject to expedited reporting to the Medicines and Healthcare Products Regulatory Agency (MHRA). The Sponsor will inform the MHRA, the REC and the Sponsor of SUSARs within the required expedited reporting timescales.”

5.2.4 Notification of deaths

Only deaths that are assessed to be caused by the study medications (Triamcinolone and Lidocaine) will be reported to the sponsor. This report will be immediate.

5.2.5 Pregnancy reporting

Pregnancy is not considered an AE unless a negative or consequential outcome is recorded for the mother or child/foetus. If the outcome meets the serious criteria, this would be considered an SAE.

5.2.6 Overdose

Any overdoses of the study medication will be reported to the CI immediately and will be recorded as protocol non-compliance and as an AR/SAR if an untoward reaction is observed.

5.2.7 Reporting urgent safety measures

If any urgent safety measures are taken the CI/Sponsor shall immediately and in any event no later than 3 days from the date the measures are taken, give written notice to the MHRA and the relevant REC of the measures taken and the circumstances giving rise to those measures.

Please refer to the following website for details on clinical trials safety reporting:
<http://www.mhra.gov.uk/Howweregulate/Medicines/Licensingofmedicines/Clinicaltrials/Safetyreporting-SUSARSandASRs/index.htm>

5.3 RESPONSIBILITIES

5.3.1 Principal Investigator (PI):

Checking for AEs and ARs when participants attend for treatment / follow-up.

1. Using medical judgement in assigning seriousness, causality and expectedness using the Reference Safety Information approved for the trial.
2. Using medical judgement in assigning seriousness and causality and providing an opinion on expectedness using the Reference Safety Information approved for the trial.
3. Ensuring that all SAEs and SARs (including SUSARs) are recorded and reported to the Sponsor within 24 hours of becoming aware of the event and provide further follow-up information as soon

as available. Ensuring that SAEs and SARs (including SUSARs) are chased with Sponsor if a record of receipt is not received within 2 working days of initial reporting.

4. Ensuring that AEs and ARs are recorded and reported to the Sponsor in line with the requirements of the protocol.

5.3.2 Chief Investigator (CI) or delegate:

1. Clinical oversight of the safety of patients participating in the trial, including an ongoing review of the risk / benefit.
2. Using medical judgement in assigning seriousness, causality and expectedness of SAEs where it has not been possible to obtain local medical assessment.
3. Using medical judgement in assigning expectedness.
4. Immediate review of all SUSARs.
5. Review of specific SAEs and SARs in accordance with the trial risk assessment and protocol as detailed in the Trial Monitoring Plan.

5.3.3 Sponsor:

1. Acknowledgement of reported SAEs, SARs and SUSARs according to the trial protocol.
2. Expedited reporting of SUSARs and Urgent Safety Measures to the Competent Authority (MHRA in UK) and REC within required timelines.
3. The unblinding of a participant for the purpose of expedited SUSAR reporting.
4. Checking for (annually) and notifying PIs of updates to the Reference Safety Information for the trial.
5. Preparing standard tables and other relevant information for annual reports in collaboration with the CI and ensuring timely submission to the MHRA and REC.

6. ASSESSMENT AND FOLLOW-UP

The end of the trial will be when the patient has completed all pain VAS scores for the documented time points (pre-injection, time of injection, 5-minutes after the injection, 1-hour, 2-hour, 3-hour and 24-hour post injection), answered the three additional questions and returned the form by post.

7. STATISTICS AND DATA ANALYSIS

7.1 DESCRIPTION OF STATISTICAL METHODS

The primary objective;

Investigate whether there is a difference in pain VAS scores at 1-hour after a corticosteroid injection for trigger finger, de Quervains tenosynovitis or carpal tunnel syndrome administered with or without local anaesthetic.

Primary outcome measure of primary objective:

1a) A analysis of the mean change in pain VAS score between 1-hour post injection and baseline pre-injection will be performed. The primary intention will be the use of parametric tests

(Unpaired Students T-test) dependent upon the assessment of score distribution (skewness and kurtosis). Non-parametric testing will be employed if the mean distribution fails tests of normality.

Secondary outcome measures of primary objective:

1b) The effect size at 1-hour post injection will be calculated to measure the significance of the difference between the study and control group.

Mean score at 1-hour in corticosteroid alone group	-	Mean score at 1-hour in corticosteroid and LA group
Standard deviation		

The objectives;

i) Additional sensitivity analysis will be conducted to investigate whether there is a difference in pain VAS scores during the 24-hours after a corticosteroid injection for trigger finger, de Quervains tenosynovitis or carpal tunnel syndrome administered with or without local anaesthetic.

Outcome measure: The cumulative pain in the 24-hour period in both groups will be calculated by using the area under the curve. Multilevel linear regression analysis will be conducted to compare 24 hour pain VAS with injection intervention nested in patient condition.

ii) Additional sensitivity analysis will be conducted to investigate whether there is a difference in the pain VAS scores at the time of the corticosteroid injection for trigger finger, de Quervains tenosynovitis or carpal tunnel syndrome administered with or without local anaesthetic.

Outcome measure: the pain VAS scores in each group at the time of the injection. Multilevel linear regression analysis will be conducted to compare pain VAS with injection intervention nested in patient condition.

iii) Investigate the difference in the additional analgesia required and in the functional use of the hand during the first 3 hours following a corticosteroid injection for trigger finger, de Quervains tenosynovitis or carpal tunnel syndrome administered with or without local anaesthetic.

Outcome measure: The percentage of patients requiring additional analgesia or who experienced worsening hand function will be determined from the three questions asked in the patient assessment record. The results will be presented as numbers with additional details given in the patients' response, but no statistical analysis will be performed on these results.

No interim or subgroup analysis will be performed.

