Patients will be randomised using the simple randomisation service provided by Sealed Envelope Ltd. This is an online service that provides random permuted block randomisation, ensuring participants are balanced between the control and treatment group. The physician will use a unique URL and password to randomise patients in A (treatment) or B (control) group.

Patients will receive injections containing one of the two following solutions, delivered under landmarks guidance to treat either; trigger finger, de Quervains tenosynovitis or carpal tunnel. Both combinations are used as part of routine practice for soft tissue corticosteroid injections in the hand and wrist at University Hospital NHS Trust by the local Hand and Wrist surgeons:

- A. 1ml of triamcinolone (40mg/1ml)
- or
- B. 1ml of triamcinolone (40mg/1ml) + 1ml 1% Lidocaine

The registrar will draw up, prepare the treatment in a separate room so that the patient will remain blinded. Neither treatment can be distinguished from one another by their appearance alone.

During the clinic appointment the patient will complete a pain VAS score prior to the injection, for pain experience at the time of the injection and at 5 minutes post injection on the patient assessment record. The pain VAS score of the pain experience during the corticosteroid steroid will be recorded immediately after the procedure. The patient then takes the patient assessment record home to complete further pain VAS scores at; 1-hour, 2-hour, 3-hour and 24-hours following the injection. The timings at which these scores must be recorded will be clearly documented on the patient assessment record by the physician before leaving clinic to help remind the patient. There are three further questions, on the same form; that the patient will be required to answer at 3-hours post injection (Appendix 4).

During the first 3-hours after your steroid injection:

1. Did you take any additional painkillers because of pain at the injection site?

YES Medication: _____

Time taken: _____

NO (go to next question)

2. Did you have any reduction in hand function, below normal, as a result of the injection?

YES please describe your reduction in function:

NO

3. Did you experience any new numbness in your hand, as a result of the injection?

YES

NO

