After the final pain VAS score at 24-hours the patient will receive a follow-up call by the registrar to ensure the assessment form has been completed, to answer any questions and remind the patient to

[figure not shown]
return the form using the prepaid envelope provided. After the form is posted the patients participation in the study will be complete.

The routine dictated clinic letter completed by the physician will outline the patients diagnosis, inclusion into the trial, and an overview of the trial and the consent process, but will not specify which treatment was delivered. A copy of this letter is kept in the patients' notes and a copy is sent to the GP.

The patient participation record and a copy of the consent form will be kept in the site file and stored in a locked filling cabinet in [name], Level 11, Derriford Hospital.

Returned patient assessment records will be collected by the departmental secretary, held within the site file and remain sealed until the end of recruitment. Once the recruitment phase is completed the patient assessment records will be open and the pain VAS scores will be measured, recorded on an excel spread sheet then statistically analysed by a blinded assessor ([name] - A member of the study management team, but directly not involved in patient recruitment). The same individual, who will not be involved in patient recruitment, will take all the measurements. Measurements will be taken using a standard 20cm ruler with 1mm increments and recorded to the nearest. Incomplete patient assessment records will be included on an intention to treat basis. A summary of the investigations, treatment and assessment can be found in Appendix 5. A planned time for the SToICAL study is outline in a Chart (Appendix 6)

Patient recruitment process during outpatient clinic:

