7.2 THE NUMBER OF PARTICIPANTS

Minimally clinical important difference of 20mm will be used as the clinically admissible margin of non-inferiority. From previous studies, it is assumed to use a standard deviation of 25mm and with a 95% power calculations have determined a required sample size of 41 per study arm, when including a 20% fall out rate a total sample size of 100 patients will be required²².

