7.3 THE LEVEL OF STATISTICAL SIGNIFICANCE

. All statistical testing was done at the two-sided 5% significance level, and 95% CIs with Stata 14.2.

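### Low-cost improvement: analyse 1-hour VAS by ANCOVA on baseline VAS, and keep a difference in mm to set against the 20 mm margin if normality fails

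*Combined protocol and SAP*

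**What the plan says.** Section 7.1 (1a) defines the primary analysis: "1a) A analysis of the mean change in pain VAS score between 1-hour post injection and baseline pre-injection will be performed". The intended test is an unpaired Student's t-test with no covariate. The choice of test depends on the observed distribution: "Non-parametric testing will be employed if the mean distribution fails tests of normality". Neither the alternative test nor an estimator to go with it is named.

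Section 7.2 sets the criterion: "Minimally clinical important difference of 20mm will be used as the clinically admissible margin of non-inferiority". It assumes an SD of 25 mm, without saying whether this is the SD of a single score or of the change, and gives 41 per arm for 95% power. Section 7.3 adds: "All statistical testing was done at the two-sided 5% significance level, and 95% CIs with Stata 14.2". Section 1.1 describes the one-sided non-inferiority idea and a zone of indifference below 20 mm. No section states which confidence limit is compared with 20 mm.

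Baseline pain is recorded in clinic (section 3): "the patient will complete a pain VAS score prior to the injection". Measure 1b is a standardised difference of raw 1-hour means: "The effect size at 1-hour post injection will be calculated to measure the significance of the difference between the study and control group".

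**The concern.** There are two separate points.

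**Route to the margin.** A non-inferiority conclusion against 20 mm needs a difference in mm with a confidence interval. A rank test of no difference gives a p-value against equality. A non-significant result would not show non-inferiority, and a significant one would not show a deficit of 20 mm. A Hodges-Lehmann shift with its interval could fill the gap, but the plan does not specify one. Measure 1b cannot fill it, because it is in SD units. If the normality check fails, the primary question could be left without a pre-specified answer.

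**Precision.** A t-test on change is a regression of the 1-hour score on treatment with the baseline coefficient fixed at 1. If the best coefficient is well away from 1, the interval is wider than the same data could give. ANCOVA estimates that coefficient.

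**Working it through.** **Inputs.** From sections 7.2 and 7.3: margin 20 mm, SD 25 mm, 41 per arm (82 analysed), two-sided 5% (one-sided 2.5% for non-inferiority). Assumed, because the documents do not give them: true difference 0; correlation ρ between baseline and 1-hour VAS of 0.3, 0.5 or 0.7; baseline SD (SDb) of 15, 25 or 30 mm against a 1-hour SD (SD1) of 25 mm; the same slope and SD in both arms.

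**The plan's own figure.** n per arm = 2 × 25² × (1.96 + 1.645)² / 20² = 40.6, so the stated 41 reproduces. Exact t-test power at 41 per arm with SD 25 mm is 94.7%.

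**SD under each analysis.**
- Change score: √(SDb² + SD1² − 2ρ·SDb·SD1), 80 df.
- ANCOVA: SD1·√(1 − ρ²), 79 df.
- The first variance minus the second is (SDb − ρ·SD1)². This is never negative, and is zero only when the best coefficient, ρ·SD1/SDb, equals 1.

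**Cost of estimating the coefficient.** For k covariate coefficients, the expected standard error is inflated by √(1 + k/(82 − k − 3)). For k = 1 this is √(1 + 1/78) = 1.0064. With the slightly larger t quantile, the worst-case ratio of widths is 1.0066, about 0.7% wider. If condition is added as a three-level factor (k = 3, 77 df), the worst case is 1.0202, about 2.0% wider.

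**Expected 95% CI half-width at 41 per arm, SD1 = 25 mm**

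| SDb (mm) | ρ | Change score (mm) | ANCOVA, baseline only (mm) | Narrower by |
|---|---|---|---|---|
| 25 | 0.3 | 13.00 | 10.55 | 18.8% |
| 25 | 0.5 | 10.99 | 9.58 | 12.8% |
| 25 | 0.7 | 8.51 | 7.90 | 7.2% |
| 15 | 0.3 | 10.99 | 10.55 | 4.0% |
| 15 | 0.5 | 9.58 | 9.58 | 0.0% |
| 15 | 0.7 | 7.92 | 7.90 | 0.3% |
| 30 | 0.3 | 14.41 | 10.55 | 26.8% |
| 30 | 0.5 | 12.24 | 9.58 | 21.7% |
| 30 | 0.7 | 9.58 | 7.90 | 17.5% |

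Simulation with 20,000 trials per scenario agreed with the narrowing to within 0.1 percentage points.

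**Power (noncentral t, covariate cost included).**
- If 25 mm is the SD of the change: 94.7% for the planned test at every ρ. For ANCOVA at ρ = 0.3, 0.5 and 0.7: 99.3%, 98.4% and 97.1% with equal SDs; 96.1%, 94.7% and 94.8% if the baseline SD is 0.6 of the 1-hour SD.
- If 25 mm is the SD of a single score: at ρ = 0.3 with equal SDs, 85.6% for the planned test against 96.1% for ANCOVA; at ρ = 0.3 with baseline SD 30 mm, 77.9% against 96.1%; at ρ = 0.5 with baseline SD 15 mm, 98.4% for both.

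**Adding condition (assumed to have no effect).** The narrowing falls slightly, for example from 18.8% to 17.8% with equal SDs and ρ = 0.3. With baseline SD 15 mm and ρ = 0.5 the interval becomes 1.3% wider than under the planned test. If 25 mm is the change SD, power in that case (SD ratio 0.6, ρ = 0.5) is 94.2% against 94.7%.

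**The case against.** The strongest reply is that nothing is broken. Randomisation makes the change-score t-test unbiased, the sample size reproduces, and power is 94.7% on the plan's own inputs. The precision gain rests on a correlation and a baseline SD that the documents do not give, and over the assumed range it runs from 0.0% to 26.8%. The larger power contrasts also need 25 mm to be a single-score SD. All of this stands. It is why the point is an improvement, and no power shortfall is claimed.

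A second reply is that the missing estimate in mm does not require ANCOVA: keeping the mean difference in change, with a robust or bootstrap interval, would close that gap. This is also correct. The two changes are separable, and ANCOVA is the better choice of estimate rather than the only one.

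A third reply is that the framework is fuller than section 7.1 suggests, since section 1.1 describes the one-sided comparison and section 7.3 refers to 95% CIs for all testing. That supports the intended logic, but it supplies neither an estimator for the non-parametric route nor an explicit rule linking a confidence limit to 20 mm.

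Finally, adjusting for condition can slightly reduce power, so it should remain optional.

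**Conclusion.** The point holds as an improvement that should be made; it is not an error or a bias. The gap on the non-parametric route follows from the text and needs no assumption: no estimate in mm is specified there. The precision argument is one of bounded cost and possible benefit. At 41 per arm with a common slope and SD in both arms, baseline-only ANCOVA widens the expected interval by at most about 0.7%, whatever the correlation and SD ratio. If the change SD is 25 mm and the SDs are equal, the half-width falls from 11.0 mm to 8.9, 9.6 or 10.2 mm at ρ = 0.3, 0.5 or 0.7. Where the best coefficient is close to 1 there is practically no gain. The actual size cannot be settled from the documents.

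**What to change.** In section 7.1, replace 1a with a linear model of 1-hour VAS on treatment and baseline VAS. Report the adjusted mean difference, steroid alone minus steroid plus lidocaine, in mm with its two-sided 95% CI. State that non-inferiority is concluded if the upper limit is below 20 mm. If normality is doubtful, keep this estimate and use a robust or bootstrap CI. Keep the change-score analysis as a sensitivity analysis.

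Optional additions:
- Add condition as a three-level factor. The secondary models already need it ("Multilevel linear regression analysis will be conducted to compare pain VAS with injection intervention nested in patient condition"), and the clinic letter "completed by the physician will outline the patients diagnosis". No stratification by condition is described, and the gain cannot be computed.
- Base 1b on the adjusted difference. In the same patients, its present numerator differs from the 1a difference by the observed baseline difference; partially completed forms (section 7.6) may also make the two patient sets differ.
- State in section 7.2 which SD the 25 mm is.

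**Cost.** One degree of freedom (80 to 79), or three (80 to 77) with condition. No new data are needed, and a patient without a baseline score is lost to 1a and to a complete-case ANCOVA alike. The change needs a protocol amendment with HRA review and R&D acceptance (section 9.1). Section 3 keeps the returned assessment records sealed until recruitment ends, so the change can be made before these data are seen.
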